## PROTOCOL

Title: Ventilation During Intensive Care Unit Transport After Cardiac Surgeries; When Should we Use a Ventilator?

This study was approved by the institutional review board of Thomas Jefferson University (iRISID-2023-1921), and verbal informed consent was obtained from all participants before enrollment. The trial was registered at ClinicalTrials.gov (NCT06006208) on August 23, 2023

### Study design

This single-center, prospective clinical trial was conducted at a tertiary academic hospital.

### Study participants

Patients aged > 18 years who underwent full sternotomy cardiac surgery and required postoperative ICU care were included in the study. The exclusion criteria included extubation in the operating room, postoperative need for mechanical circulatory support, postoperative open chest, and continuous inhalation of epoprostenol or nitric oxide.

For data analysis population, patients who needed to be switched the ventilation method from the originally designated method were excluded.

Eligible patients were randomized to either (1) manual ventilation using an AMBU bag (AMBU, Copenhagen, Denmark) or (2) mechanical ventilation using a Hamilton C1 ventilator (Hamilton Medical, Reno, NV) during transport to the ICU. Each participant provided verbal consent without knowing which arm they were assigned to. The anesthesiologist made the final decision regarding the ventilation modality based on the post-cardiopulmonary bypass biventricular function and PaO2/FiO2 or PaCO2 levels.

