### Primary outcomes

The primary outcomes included hemodynamic parameters before and after ICU transport. Hemodynamic indices mean arterial pressure (MAP). Pre-transport hemodynamic values were averaged from the final three readings (taken at 1-min intervals) before switching to the transport monitor, and post-transport readings were recorded immediately after transfer to the ICU monitor. Significant hypotension was defined as > 20% decrease in MAP between pre- and post-transport. The transport time began when the patient was switched to manual or mechanical ventilation and ended when the patient was switched to an ICU ventilator.

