### Secondary outcomes

The secondary outcomes were the change in PaO2/FiO2 ratio, PaCO2 levels, and biventricular function before and after ICU transport. Pre-transport arterial blood gas (ABG) samples were obtained when the patient was ready to leave the operating room, and post-transport ABG samples were collected immediately upon arrival in the ICU. Left ventricular (LV) and right ventricular (RV) functions were visually assessed using VScan AIR SL (GE Medical, IL) transthoracic echocardiography (TTE) in the apical four-chamber and parasternal mid-papillary short-axis views before and after transport. Biventricular function was graded as moderate-to-severe hypokinesis (grade 1), mild hypokinesis (grade 2), normal (grade 3), or hyperkinesis (grade 4).

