#### Sample size determination and statistical analysis

Sample size calculations were based on prior clinical experience and data from a previous study. We hypothesized that 0% of patients receiving mechanical ventilation would experience a decrease in MAP during transport compared with 28% of those manually ventilated with an AMBU bag. With an alpha level of 0.05 and 90% power, we estimated that 38 patients per group (N = 76) would be required.

Summary statistics are presented for the demographic and clinical variables in each group. Continuous variables are expressed as mean  $\pm$  standard deviation (SD) or median (interquartile range [IQR]), as appropriate. Categorical data are summarized as frequencies

and percentages. Group comparisons were performed using the independent t-test or Mann–Whitney U test for continuous variables. Correlations between two continuous variables were assessed using Pearson's or Spearman's rank correlation test. Receiver operating characteristic (ROC) curve analysis was used to assess the accuracy of the predictive value of SVR for > 20% drop in MAP. Statistical significance was set at  $p < 0.05$ . All statistical analyses were performed using EZR (Saitama Medical Center, Jichi Medical University, Saitama, Japan), a graphical user interface for R (R Foundation for Statistical Computing, Vienna, Austria). More precisely, this is a modified version of R commander designed to add statistical functions that are frequently used in biostatistics.

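### The only analysis population drops patients switched from their assigned ventilation method, and no as-randomised analysis is planned, so the comparison is open to selection bias of unknown size and direction

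*Combined protocol and SAP*

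**What the plan says.** The section on study participants states the allocation ("Eligible patients were randomized to either (1) manual ventilation using an AMBU bag") and, just before it, the analysis set: "For data analysis population, patients who needed to be switched the ventilation method from the originally designated method were excluded". No other analysis population is defined. The statistical section lists summaries, group comparisons, correlations and a ROC curve. It mentions no intention-to-treat or as-randomised set, no sensitivity analysis and no allowance for excluded patients.

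The same participants section adds: "The anesthesiologist made the final decision regarding the ventilation modality based on the post-cardiopulmonary bypass biventricular function" and on blood gases. It does not say when this decision falls relative to randomisation, or whether it is what produces a switch.

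The outcomes affected are the MAP event ("Significant hypotension was defined as > 20% decrease in MAP between pre- and post-transport") and, among the secondary outcomes, changes in blood gases and "biventricular function before and after ICU transport".

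**The concern.** A patient can be switched from a designated method only after one has been designated, so the exclusion acts after assignment. The sentence ties it to need, not to chance. If need is related to prognosis, the patients left in the two arms may differ in condition before transport.

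If the anesthesiologist's decision is the switch, exclusion depends on the same measurements that serve as secondary outcomes and that plausibly predict a fall in MAP. The documents do not state that link, and the concern does not need it: the exclusion sentence alone is enough.

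The direction of bias depends on the outcome. An arm that loses its sickest patients looks better on the MAP event if sicker patients have more events. The same arm looks worse on change in PaO2/FiO2, because those who remain start higher and regress towards the mean.

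**Working it through.** **The plan's own figure.** The inputs are 28% vs 0%, alpha 0.05 and 90% power. The test is taken as two-sided because sidedness is not stated. Without continuity correction, n = [1.960·√(2·0.14·0.86) + 1.282·√(0.28·0.72)]² / 0.28² = 30.1, so 31 per group. The corrected value is (30.1/4)·[1 + √(1 + 4/(30.1·0.28))]² = 36.9, so 37. The plan's 38 is thus reproduced to within one patient (exactly 38 if the zero rate is entered as 0.1%). It leaves no stated allowance for exclusions.

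**Simple identity.** If a share s of one arm is switched and has event risk r, and the whole arm has risk p, the analysed rate is (p − s·r)/(1 − s). Take no true effect, with p = 28% in both arms, and assume s and r:

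- s = 10%, r = 56%: (0.28 − 0.056)/0.9 = 24.9%, a false difference of −3.1 points.
- s = 20%, r = 84%: (0.28 − 0.168)/0.8 = 14.0%, a false difference of −14.0 points.
- s = 20%, r = 0%: 0.28/0.8 = 35.0%, a false difference of +7.0 points.

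The sign follows the risk of those removed, which the documents do not give.

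**Severity model.** Severity and event are linked by a bivariate normal distribution with assumed correlation 0.3, 0.45 or 0.6. The null event rate is 14%, the midpoint of 0% and 28%, taken to apply to the >20% drop. (The sample-size hypothesis speaks of a decrease without that threshold.) 38 per arm are assumed randomised, so 34 or 30 remain after 10% or 20% are dropped. Rejection rates are for the two-sided Fisher test at 0.05, chosen here because the plan names no test for proportions.

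| Assumed exclusion | 10% dropped | 20% dropped |
|---|---|---|
| Sickest, one arm, no effect: analysed rate (true 14%) | 12.4 / 11.4 / 10.2% | 11.3 / 9.7 / 7.9% |
| – false-positive rate | 3.6 / 4.1 / 5.0% | 3.2 / 4.1 / 6.1% |
| – same sizes, correlation 0 | 3.4% | 3.2% |
| Sickest in one arm, least sick in the other, no effect: false gap | 2.6 / 3.9 / 5.3 points | 4.7 / 7.0 / 9.4 points |
| Sickest, both arms, true 28% vs 0%: manual rate analysed | 25.8 / 24.6 / 23.2% | 24.2 / 22.0 / 19.6% |
| – power | 91 / 87 / 83% | 77 / 67 / 55% |
| – same sizes, correlation 0 | 94% | 88% |

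With no exclusion, the false-positive rate is 2.3% and power is 97%. Equal exclusion of the sickest from both arms gives no bias when there is no effect. At correlation 0 there is no bias in any row. Equal numbers excluded per arm do not guarantee safety, as the opposite-ends row shows.

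**Change in PaO2/FiO2 (secondary).** Bias in baseline SD units = c·(0.6 − 1)·φ(z_q)/(1 − q). Here 0.6 is the assumed pre/post correlation with equal SDs, q is the share dropped at the low end, and c = 0.5 to 1.0 is the assumed correlation of the deciding value with baseline. For q = 10%: 0.4·0.1755/0.9 = 0.078 at c = 1, so 0.04–0.08 SD. For q = 20%: 0.4·0.2800/0.8 = 0.140, so 0.07–0.14 SD. The depleted arm looks worse. Simulated t-test error is 5.5–6.8% and 6.3–10.4%.

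**The case against.** The strongest reply has four parts.

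*Size and mechanism are conjecture.* No switch rate, arm, reason or timing is given. If switches are rare or unrelated to outcome, the bias is negligible. This stands as a limit on the size. It does not rescue the rule: with no switches the two analyses coincide and the change costs nothing, and with some switches the reader needs them counted by arm.

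*Part of the apparent harm is sample size.* This is right. Unequal group sizes alone raise the false-positive rate from 2.3% to 3.4% or 3.2%, and random loss from both arms alone cuts power from 97% to 94% or 88%. Only the remainder is selection. At correlation 0.3 with 20% dropped from one arm, the false-positive rise due to selection is nil.

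*The 38 per group may mean analysed patients.* The plan does not say. If it does, power in the both-arms case is 95–90% (10% dropped) or 92–78% (20%), not 91–83% or 77–55%. The shrinkage of the manual rate is unchanged.

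*For an exposure lasting only the transport, the effect of the method actually used is a fair question.* It is, and the set without switches can address it as a supporting analysis. It should not be the only analysis of a randomised comparison.

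**Conclusion.** The concern holds and must be fixed. That the plan has no as-randomised analysis, and that its one population excludes patients on a post-assignment need, follows directly from the text, with high confidence. The rule governs every between-arm result, and with 38 per group, four exclusions are 4/38 = 10.5% of an arm.

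Confidence in size and direction is low, because every bias figure rests on assumed switch rates, risks and correlations. Within those assumptions, the MAP-event difference is distorted by anything from nothing to 14 points in either arm's disfavour, depending on who is switched and from which arm. For that outcome the main harm is a biased estimate: with the sickest dropped from one arm under the severity model, the false-positive rate passes 5% in one of six scenarios.

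**What to change.** Replace the analysis-population sentence with wording such as:

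> The primary analysis includes all randomised patients who meet the eligibility criteria of this section, including every listed postoperative exclusion applied without regard to arm, analysed in the arm to which they were randomised whatever ventilation they received.

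Keep the set without switches as a labelled per-protocol sensitivity analysis. Report the number, direction and reasons of switches by arm. State when the anesthesiologist's decision falls relative to randomisation and whether it counts as a switch.

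**Cost.** This is a wording change if outcomes of switched patients were kept, which the documents do not say. If they were not, report how many are missing by arm and bound the MAP-event difference by counting them all as events and then all as non-events. The bounds are wide: 4 or 8 missing of 38 moves that arm's rate over 4/38 = 10.5 or 8/38 = 21.1 points.

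The as-randomised effect is also diluted if switching is common. Suppose switched patients carry the risk of the method received, so a share s switching both ways gives 28%·(1 − s) vs 28%·s:

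- s = 5%, 10% or 20% lowers Fisher power at 38 per arm from 97% to 89%, 77% or 45%.
- Regaining 90% takes 52 per arm at 10% and 93 at 20%.
- One-way switching of 10% (20%) leaves 94% (88%) if manual to ventilator, and 85% (69%) if ventilator to manual.

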#### Anesthesia and ventilation protocols

General anesthesia was induced via endotracheal intubation, and arterial, central venous, and pulmonary arterial lines were placed alongside the transesophageal echocardiography. The selection of anesthetic agents, inotropes, vasopressors, transfusion strategies, and fluid management was at the discretion of the attending anesthesiologist. Dexmedetomidine 0.7–1.0 mcg/kg/h was used for sedation during the transport to the ICU.

For manual ventilation, the AMBU bag technique, including the PEEP valve setting (5–10 cmH2O), was performed by each anesthesiologist. For mechanical ventilation using the Hamilton C1 ventilator, the respiratory therapist configured the ventilator to deliver a tidal volume and respiratory rate consistent with the final operating room settings (tidal volume: 6–8 mL/ideal body weight [kg], respiratory rate: 14–16 breaths/min, PEEP: 5–10 cmH2O, and FiO2:100%). Airway pressure and end-tidal CO2 levels were not monitored during transport.

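### The anesthesiologist can override the randomised modality on post-bypass findings, with no concealment described, and the time of randomisation is ambiguous

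*Combined protocol and SAP*

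**What the plan says.** All the key statements but three are in the Study participants section of the combined protocol and SAP.

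- Allocation: "Eligible patients were randomized to either (1) manual ventilation using an AMBU bag" or to a transport ventilator. No time point, sequence generation or concealment method is given.
- Consent: "Each participant provided verbal consent without knowing which arm they were assigned to". The opening paragraph of the protocol adds that "verbal informed consent was obtained from all participants before enrollment".
- Exclusions: "The exclusion criteria included extubation in the operating room, postoperative need for mechanical circulatory support, postoperative open chest", together with continuous inhaled epoprostenol or nitric oxide.
- Modality received: "The anesthesiologist made the final decision regarding the ventilation modality based on the post-cardiopulmonary bypass biventricular function" and on PaO2/FiO2 or PaCO2.
- Analysis population: "patients who needed to be switched the ventilation method from the originally designated method were excluded".

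The Secondary outcomes section takes the change in PaO2/FiO2, PaCO2 and biventricular function across transport as the secondary outcomes. Anesthesia and ventilation protocols says that bag ventilation "was performed by each anesthesiologist", so that person knows the arm by departure at the latest. Only the participant is described as unaware of it.

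**The concern.** Randomisation protects a comparison when suitability is settled before the arm is known and the arm then stands. Here a method is designated, and afterwards a clinician reads the patient's cardiac function and gas exchange and decides what is used. If that decision departs from the allocation more often in one arm, or for different kinds of patient in each arm, the groups at departure can differ in cardiac and respiratory status. The comparison of MAP and of the secondary outcomes would then mix the effect of the modality with the reasons for choosing it.

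A second route is possible but less certain. If the arm already existed at consent, the four exclusions were applied after assignment. At least two of them, extubation in the operating room and starting an inhaled vasodilator, are choices of the treating team. Entry as well as treatment could then depend on knowledge of the arm.

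This is distinct from the rule that drops switched patients. Analysing everyone as assigned would bring the switched patients back. It would not restore concealment, recover patients excluded after assignment, or undo the contrast lost to overrides.

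**Working it through.** **Order of steps, from the text**

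1. Override. One sentence refers to a method designated at the outset and to patients switched from it; another gives the anesthesiologist the last word on post-bypass findings. Together they place the decision after allocation, whenever allocation took place.
2. Entry, reading A. Eligible patients are randomised, and inclusion is worded in the past tense (surgery already undergone). This fits allocation after the exclusions.
3. Entry, reading B. The consent sentence speaks of an arm that has been assigned. Consent is verbal, from the participant and before enrolment, so presumably before anesthesia. The exclusions become known only at or after the end of surgery. This fits allocation before the exclusions.
4. Under A only the override remains. Under B the exclusions also follow assignment. Neither reading comes with a described concealment step.

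**The plan's own figure**

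Inputs from Sample size determination and statistical analysis: the hypothesis that "0% of patients receiving mechanical ventilation would experience a decrease in MAP during transport", against 28% with the bag; alpha 0.05; power 90%; 38 per group. The two-sided normal approximation with continuity correction gives 37 per group (31 without correction). The stated 38 reproduces closely, and sample size is not the issue.

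**Illustrations (override and late-exclusion rates are assumed; the documents give none)**

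*(i) Selective removal from the manual arm, plan's event rate.* Expected events: 38 × 0.28 = 10.64. Removing k patients at risk r leaves a rate of (10.64 − k·r)/(38 − k).

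| k | r | Manual rate | Power against 0/38 (Fisher, two-sided) |
|---|---|---|---|
| 0 | – | 28.0% | 97.4% |
| 4 | 0.6 | 8.24/34 = 24.2% | 97.9% |
| 4 | 0.8 | 7.44/34 = 21.9% | 95.8% |
| 6 | 0.6 | 7.04/32 = 22.0% | 94.3% |
| 6 | 0.8 | 5.84/32 = 18.2% | 86.1% |

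The 97.9% slightly exceeds the planned 97.4% because Fisher's test is discrete and the arms have become unequal.

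*(ii) Overridden patients kept in their assigned arm.* If moving patients to the ventilator averts 20% of the manual arm's events, its rate is 0.28 × 0.8 = 22.4%, and power is 88.3%.

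*(iii) No true effect.* Both arms are at 28%, and 30% of patients are high-risk with event rate h. The low-risk rate is (0.28 − 0.3h)/0.7, which is 18.6% for h = 0.5 and 14.3% for h = 0.6. If a fraction s of high-risk patients leaves the manual arm only, its rate is [0.3(1 − s)h + 0.28 − 0.3h]/[0.3(1 − s) + 0.7].

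- h = 0.5, s = 0.25: 0.2425/0.925 = 26.2%, a difference of −1.8 points.
- h = 0.6, s = 0.75: 0.145/0.775 = 18.7%, a difference of −9.3 points.

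These are spurious differences of about 2 to 9 points. Removal from the ventilator arm instead gives the opposite sign.

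**The case against.** The strongest reply is that much of this is inference. Several stronger readings are tempting, and the documents do not support them.

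- *A reader might infer that the arm was definitely assigned before the exclusions were known.* No sentence times randomisation. The consent sentence may mean only that participants were not told their arm, and randomising eligible patients fits allocation after the exclusions. The entry part is an ambiguity, not an established fact.
- *A reader might infer that the findings behind the override are the baseline values of the secondary outcomes.* The variables are the same, but the measurements may not be. The secondary-outcome baselines are a blood gas drawn at readiness for departure and handheld transthoracic grades before transport. The override refers only to post-bypass findings, and transesophageal echocardiography was also in place.
- *A reader might infer that sicker patients were moved from bag to ventilator, or were made ineligible because of their arm.* The text gives the criteria for the decision but no direction. Nothing in it suggests that a team extubated a patient or started an inhaled vasodilator on account of the allocation.
- *A reader might take the figures as an estimate of bias.* Counts, risks and one-sidedness are all assumed. Scenarios (i) and (ii) shrink the difference that the plan expects, so they do not produce a false positive, and power mostly stays high. The removal figures in (i) and (iii) also partly reflect the separate rule that drops switched patients.

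All of these limits stand. None of them touches the override itself, which the text states and which holds under either reading of the timing.

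**Conclusion.** The concern holds for the modality received. As written, a clinician from whom no step conceals the arm makes the last decision after allocation, on variables shared with the secondary outcomes and plausibly prognostic for MAP. That is more than missing detail, because following the text lets prognosis decide the treatment. For entry, the plan is ambiguous, and the concern holds only if the arm existed before the end of surgery.

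Size and direction cannot be derived from the documents. The manual-arm rates of about 18% to 24% instead of 28%, and the null difference of about 2 to 9 points, show what assumed patterns would do and predict nothing. The main threat is bias, which a larger sample would not remove; dilution of the contrast is secondary.

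**What to change.** Reconcile randomisation with the anesthesiologist's final decision in Study participants by stating the steps in order:

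1. Obtain verbal consent with no arm assigned.
2. At the end of surgery, check the four exclusions and record whether the anesthesiologist judges either modality acceptable for this patient.
3. Log patients for whom one modality is judged necessary, and do not randomise them.
4. Only then reveal a concealed allocation, for example by sealed envelope or electronic list.

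Later changes of modality remain the anesthesiologist's clinical decision. Record each with its reason and report them by assigned arm. State that the conclusions apply to patients for whom either modality was acceptable.

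Cost: protocol wording, a short log and a later moment of disclosure. Some consented patients will not be randomised, so more consents may be needed to reach 76. The respiratory therapist, who configures the transport ventilator, learns the assignment later.

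The protocol is written in the past tense. If enrolment is complete, the order of steps cannot be changed. In that case state when allocation occurred, how it was concealed and who applied the exclusions, and report late exclusions and overrides by assigned arm with reasons.

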### Primary outcomes

The primary outcomes included hemodynamic parameters before and after ICU transport. Hemodynamic indices mean arterial pressure (MAP). Pre-transport hemodynamic values were averaged from the final three readings (taken at 1-min intervals) before switching to the transport monitor, and post-transport readings were recorded immediately after transfer to the ICU monitor. Significant hypotension was defined as > 20% decrease in MAP between pre- and post-transport. The transport time began when the patient was switched to manual or mechanical ventilation and ended when the patient was switched to an ICU ventilator.

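### The hypotension event measures a relative fall in MAP, not low arrival pressure, and the arms are compared without adjusting for pre-transport MAP

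*Combined protocol and SAP*

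**What the plan says.** The Primary outcomes section of the combined protocol and SAP makes MAP the outcome: "The primary outcomes included hemodynamic parameters before and after ICU transport". It then defines an event: "Significant hypotension was defined as > 20% decrease in MAP between pre- and post-transport". The two readings are obtained differently. For the first, "Pre-transport hemodynamic values were averaged from the final three readings (taken at 1-min intervals) before switching to the transport monitor". For the second, "post-transport readings were recorded immediately after transfer to the ICU monitor", with no averaging stated.

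The section on sample size and statistical analysis makes this assumption: "0% of patients receiving mechanical ventilation would experience a decrease in MAP during transport compared with 28% of those manually ventilated with an AMBU bag". On the resulting size it says: "With an alpha level of 0.05 and 90% power, we estimated that 38 patients per group (N = 76) would be required". The assumption does not repeat the 20% threshold. The threshold returns as the outcome of the ROC analysis, which concerns the "predictive value of SVR for > 20% drop in MAP".

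For comparing the arms, the section names the t-test and the Mann–Whitney test for continuous variables. It names no test for a binary outcome and no analysis that takes pre-transport MAP into account. Neither section gives an absolute MAP level, a count of low-pressure arrivals, or a target range for MAP before transport. The section on anesthesia and ventilation leaves vasopressors, inotropes and fluids to the attending anesthesiologist.

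**The concern.** Two things follow from the definition and the analysis together.

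First, the label says more than the rule delivers. A patient who leaves at 100 mmHg and arrives at 79 has fallen 21% and is counted as significantly hypotensive. A patient who leaves at 65 and arrives at 52 has fallen exactly 20% and is not. A reader who sees only the event rate may take it as the share of patients who arrived with low pressure.

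Second, pre-transport MAP is the denominator of the event and the starting point of any MAP change, so either may vary with it. The plan collects this value but does not use it in the comparison of arms. At stake are some precision, some protection against a difference in starting pressure between the arms, and a clear reading of the result.

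**Working it through.** **The plan's own figure.** Inputs from the statistical section: 0% vs 28%, alpha 0.05 (taken as two-sided), 90% power.

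n = [1.96·√(2·0.14·0.86) + 1.2816·√(0.28·0.72)]² / 0.28² = (0.962 + 0.575)² / 0.0784 ≈ 30.1, so 31 per group.

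With the continuity correction, (30.1/4)·[1 + √(1 + 4/(30.1·0.28))]² ≈ 36.9, so 37 per group. The plan states 38. The sample size therefore reproduces and is not in question here.

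**What the rule counts.** An event requires post-MAP < 0.80 × pre-MAP. For any arrival level F, the crossover is a pre-transport MAP of F/0.80 = 1.25F. Above it, a patient can be an event while arriving at or above F. Below it, a patient can arrive below F without being an event. This is arithmetic and holds for every F.

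**Dependence on the starting value.** The documents give no MAP distribution, so these inputs are assumptions: pre-transport mean 75, SD 10 for both readings, bivariate normal, correlation ρ, and an overall rate of 28%. The 28% comes from "compared with 28% of those manually ventilated with an AMBU bag"; attaching it to the > 20% event is itself an assumption. Setting the overall rate to 28% (normal quantile −0.5828) gives

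μ_post = 0.8·75 + 0.5828·10·√(1.64 − 1.6ρ)

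P(event | pre = x) = Φ{[0.8x − μ_post − ρ(x − 75)] / [10·√(1 − ρ²)]}

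For ρ = 0.5, μ_post = 60 + 5.828·0.9165 = 65.34. At x = 65 this gives Φ[(52 − 65.34 + 5)/8.66] = Φ(−0.963) = 16.8%. At x = 90 it gives Φ[(72 − 65.34 − 7.5)/8.66] = Φ(−0.097) = 46.1%.

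| ρ | MAP 65 | MAP 75 | MAP 85 | MAP 90 |
|---|---|---|---|---|
| 0.3 | 11.9% | 25.5% | 44.7% | 55.1% |
| 0.5 | 16.8% | 26.9% | 39.3% | 46.1% |
| 0.7 | 23.3% | 27.8% | 32.7% | 35.3% |
| 0.8 | 28.0% | 28.0% | 28.0% | 28.0% |
| 0.9 | 35.6% | 27.5% | 20.4% | 17.3% |

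The rate is flat at 0.8 because the slope of post on pre then equals the 0.80 in the rule. Another model also reverses the direction. If the fall in mmHg has mean 8 and SD 12 whatever the start, P = 1 − Φ[(0.2x − 8)/12], which is 36.9% at MAP 60 and 15.9% at MAP 100.

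**Label against arrival pressure.** In the same normal model at ρ = 0.5, with 60 mmHg used purely as an illustration, 38% of events arrive at or above 60, and 42% of arrivals below 60 are not events. Across ρ from 0.3 to 0.7 the ranges are 36% to 40% and 36% to 47%.

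**Chance imbalance.** The SE of the arm difference in pre-transport MAP is 10·√(2/38) = 2.29 mmHg. A 4 mmHg difference is 4/2.29 = 1.74 SE, reached in either direction in about 8% of trials of this size. With the arm means at 75 ± 2 and no treatment effect, the rates are Φ[−0.5828 ± 2(0.8 − ρ)/(10·√(1.64 − 1.6ρ))]:

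- ρ = 0.3: 31.2% vs 25.0%
- ρ = 0.5: 30.2% vs 25.8%
- ρ = 0.7: 28.9% vs 27.1%

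That is about 2 to 6 points, against a planned difference of 28.

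**The case against.** The strongest reply is that a within-patient percentage fall is a coherent answer to what happens to MAP across transport, and it applies equally to both arms. An absolute floor has the mirror fault, since it would label a patient who left low and did not change. The plan defines its term where it uses it, MAP before and after transport is itself the primary outcome, and the pre-transport value is an average of three readings, which damps transient noise in the denominator. All of this stands. A reader might infer that the missing absolute level is an error in the endpoint. The documents do not support that: it is a choice of what to measure.

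A reader might also infer that the definition itself makes patients with a high starting pressure more likely to be events. That is not supported either. The direction depends on how post-transport MAP tracks pre-transport MAP, and the table shows it rising, flat or reversed.

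A third tempting reading is that imbalance in pre-transport MAP biases the trial. Under randomisation, chance imbalance is ordinary sampling error and its effect here is small. The anesthesiologist's final say on modality and the exclusion of switched patients (Study participants section) could disturb balance systematically, but that is a separate matter and is not evidence of imbalance in MAP.

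What the reply does not answer is why a baseline value already collected is left out of the comparison, or why a relative fall should be reported under the name hypotension.

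**Conclusion.** The point holds as one about interpretation and efficiency. The event is a measure of relative change, and the unadjusted comparison ignores a baseline value on which the event rate and the MAP change will generally depend. The documents fix neither the direction nor the size of that dependence; the percentages above rest on assumed means, SDs, correlations and normality, and on applying the 28% to the > 20% event. It is not a finding of bias, and imbalance of the size examined could not by itself produce a 0% vs 28% result. Adjustment is worth adding because it helps whichever way the dependence runs and needs no new data.

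**What to change.** **Statistical analysis section.**

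- Compare the arms on the > 20% event adjusted for pre-transport MAP, with a method that tolerates zero events in one arm, since 0% is the planning assumption for mechanical ventilation. Firth logistic regression standardised to a risk difference is one example.
- Show the raw counts beside it, because penalisation moves a zero count off zero: in the unadjusted case 0/38 becomes (0 + 0.5)/(38 + 1) ≈ 1.3%.
- Adjust the comparison of post-transport MAP for pre-transport MAP in the same way, for example by linear regression on arm and pre-transport MAP.

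**Primary outcomes section.** Call the event a relative MAP fall > 20%. Optionally, report descriptively the distribution of arrival MAP, or a count below a level that the investigators fix before comparing arms. There is no need to require every conclusion to cite both counts.

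**Cost.** One degree of freedom and one extra descriptive line; both readings are already collected. The document is written in the past tense, so if the arms have already been compared, these additions should be marked as made afterwards.
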